### 7.3.3. Laboratory Assessments

Laboratory assessments must be conducted in accordance with the Time and Events Table ([Table 19](#)).

**Table 21 Laboratory Assessments**

| Hematology                                         | Standard Chemistry  |
|----------------------------------------------------|---------------------------------|
| Hemoglobin                                         | Sodium                          |
| Hematocrit                                         | Potassium                       |
| Red blood cell count                               | Calcium                         |
| Platelets                                          | Glucose                         |
| White blood cell count with differential           | Blood Urea Nitrogen or Urea     |
| Total neutrophils                                  | Creatinine          |
| Lymphocytes                                        | AST                             |
| Monocytes                                          | ALT                             |
| Eosinophils                                        | Alkaline phosphatase            |
| Basophils                                          | Total bilirubin                 |
|                                                    | Lactate dehydrogenase           |
| Coagulation                                 | Magnesium                       |
| PT                                                 | Phosphate                       |
| PTT                                                |                                 |
| INR                                                |                                 |
| Serum Pregnancy                 |                                 |
| serum $\beta$ -hCG (human chorionic gonadotrophin) |                                 |

1. Chemistry evaluation of bicarbonate, chloride, and uric acid are not required where there are logistical constraints
2. If serum creatinine is >1.5 mg/dL, calculate creatinine clearance using standard Cockcroft and Gault method ([Appendix 2](#)).
3. Refer to Section [7.3.2](#) for further details on serum pregnancy testing.

Prior to administration of the first dose of study treatment, results of laboratory assessments should be reviewed. Any laboratory test with a value outside the normal range may be repeated (prior to the first dose) at the discretion of the investigator. A subject with a laboratory value outside the reference range(s) may be included only if the investigator and GSK Medical Monitor agree that it is unlikely to introduce additional risk factors and will not interfere with study procedures. However, subjects with laboratory values outside eligibility criteria in Section 4.1 should be excluded.

All laboratory tests with values that are significantly abnormal during participation in the study or within 30 days after the last dose of study treatment should be repeated until the values return to normal or baseline. If such values do not return to normal within a period judged reasonable by the investigator, the etiology should be identified and the sponsor notified.

#### **7.3.4. Physical Examinations**

A complete physical examination will include assessments of the head, eyes, ears, nose, throat, skin, thyroid, lungs, cardiovascular, abdomen (liver and spleen), lymph nodes, and extremities. Height and weight will also be measured and recorded. A complete physical exam including a thorough genitourinary examination for female subjects, inspection of the head and neck region, and digital rectal examination for both male and female subjects must be performed at Screening, and Month 12 or at discontinuation if discontinuation occurs prior to Month 12. If the subject has had a genitourinary and rectal exam within 6 months of screening, these assessments do not need to be repeated at screening. Physical examinations will be obtained at each time point as noted in the Time and Events Table (Table 19).

#### **7.3.5. Neurological Examinations**

Neurological exams should be performed by the Investigator as per the Time and Events Table (Table 19). Alternatively, subjects may be referred to a neurologist or neurosurgeon, at the discretion of the investigator.

A thorough neurological assessment is required at baseline focusing on:

- mental status
- cranial nerves
- motor system
- sensory system
- the deep tendon reflexes
- coordination and the cerebellum
- gait

During study conduct, an orientating neurological assessment should be conducted at the timepoints indicated in the Time and Events Table (Table 19) in order to detect potential early neurological symptoms, such as:

- Headache
- Nausea and/or vomiting
- Vertigo and/or dizziness
- Restlessness and/or irritability
- Fatigue or sleeplessness
- Hearing loss
- Muscle weakness
- Balance problems
- Speech problems
- Others

#### **7.3.6. Dermatologic Examinations**

A full skin assessment must be performed at baseline and at various timepoints throughout the study, as noted in the Time and Events Table (Table 19). Dermatologic exams should be performed by the investigator or may be referred to a dermatologist, at the discretion of the investigator. If possible, the same physician should perform each exam for the duration of the study (i.e., if the subject is referred to a dermatologist for the screening exam, the dermatologist should do all follow up dermatologic assessments) to ensure consistency between evaluations.

#### **7.3.7. Vital Signs**

Vital sign measurements will include temperature, respiratory rate, systolic and diastolic blood pressure, and pulse rate, and will be obtained at each time point as noted in the Time and Events Table (Table 19).

#### **7.3.8. Performance Status**

Eastern Cooperative Oncology Group performance status should be assessed per the Time and Event Table (Table 19).

#### **7.3.9. Electrocardiogram (ECG)**

12-lead ECGs will be obtained at screening as noted in the Time and Events Table (Table 19) during the study using an ECG machine that automatically calculates the heart rate and measures PR, QRS, QT, and QTc intervals. At each assessment a 12-lead ECG will be performed by qualified personnel at the site after at least a five-minute rest with the subject in a semi-recumbent or supine position.

### **7.3.10. Echocardiograms**

ECHO should include an evaluation for LVEF and both right- and left-sided valvular lesions. ECHO will be performed at the time points specified in the Time and Events Table (Table 19).

Additional ECHO assessments may be performed if clinically warranted.

### **7.3.11. Ophthalmic Examination**

At certain time points in the trial and if visual changes develop, an eye exam is indicated. (Refer to Section 5.7.5.4 for visual changes stopping criteria). The exam will include best corrected visual acuity, tonometry, slit lamp biomicroscopic examination, visual field examination, and dilated indirect fundoscopy with special attention to retinal abnormalities. Optical coherence tomography is strongly recommended at scheduled visits, and if retinal abnormalities are suspected. Other types of ancillary testing including color fundus photography and fluorescein angiography are also recommended if clinically indicated.

## **7.4. Pharmacokinetics**

### **7.4.1. Pharmacokinetic Endpoints**

- Brain tumors (All subjects): The concentrations and tumor tissue distribution of dabrafenib and its metabolites, including hydroxy-, carboxy, and desmethyl-dabrafenib, in samples of the resected brain metastases will be determined in all subjects. Concentration of trametinib will also be determined in Cohort B.
- Plasma (All subjects): The concentrations of dabrafenib, its metabolites, including hydroxy-, carboxy, and desmethyl-dabrafenib, and trametinib in plasma samples collected on the day of the brain tumor resection will be determined. Levels in 2 plasma samples collected before surgery and 2 samples collected after surgery will be determined to allow accurate estimate of the pharmacokinetics at the time of the tumor resection.
- Extracranial metastases (if available): The concentrations and tumor tissue distribution of dabrafenib, its metabolites, including hydroxy-, carboxy, and desmethyl-dabrafenib, and trametinib (as appropriate in Cohort B) in samples of extracranial metastases collected on the same day as the brain tumor resection will be determined.
- Cerebrospinal fluid (CSF) (in subjects who agree to optional collection of CSF): The concentrations of dabrafenib, its metabolites, including hydroxy-, carboxy, and desmethyl-dabrafenib, and trametinib (as appropriate in Cohort B), in the CSF of subjects who give consent for optional collection of this fluid at the time of brain tumor resection will be determined.

#### **7.4.2. Brain Tumor Sample Collection for Pharmacokinetics**

Tissue for pharmacokinetic analysis will be isolated from the remaining portion of the resected melanoma brain metastasis(es) that in the clinical judgment of the neurosurgeon is not required to be submitted for pathologic confirmation of CNS melanoma metastases. 100 mg to 1 gm of the remaining tissue will be snap-frozen for pharmacokinetic analysis. If the tumor is bloody, the tissue will be blotted on gauze to dry prior to snap freezing in liquid nitrogen. A second portion (up to 500 mg) of the tumor will be inserted into a tissue cassette, and embedded in Optimum Cutting Temperature (OCT) solution, and frozen. A third portion of tumor tissue (up to 100 mg) will be fixed in formalin for paraffin embedding (FFPE). Additional tumor tissue may be used to establish an immortalized cell line and/or snap-frozen. The remaining portion from the adjacent “normal” CNS tissue that has been confirmed by the neuropathologist using frozen sections OR the overlying normal CNS tissue that is required to be resected by the neurosurgeon in order to gain access to the underlying CNS melanoma metastasis will be processed in a similar fashion. The time the tumor was resected will be recorded to facilitate the comparative pharmacokinetic analyses. Concentrations of dabrafenib, its metabolites, hydroxy-, carboxy, and desmethyl-dabrafenib, and trametinib (as appropriate) and possibly other drug-related species will be quantified in the PK tissue sample by an investigative LC-MS/MS method. The spatial distribution of dabrafenib, its metabolites, hydroxy-, carboxy, and desmethyl-dabrafenib, and trametinib (as appropriate in Cohort B), and possibly other drug-related species in the tissue samples will be determined using an investigative matrix assisted laser desorption ionization (MALDI) analysis method.

#### **7.4.3. CSF Collection for Pharmacokinetics**

Collection of CSF will be an optional procedure; subjects must provide consent for this procedure. CSF will be collected either right before cutting the dura, on condition that there is no evidence of intracranial hypertension, or using the lumbar puncture approach (following completion of craniotomy and repositioning the subject while under general anesthesia during the same operation OR postoperatively), or accessing the Ommaya reservoir, if present. Three ml of CSF will be processed for pharmacokinetic analysis and quantified using an investigative LC-MS/MS method. The time of CSF collection will be recorded for the comparative pharmacokinetic analyses.

#### **7.4.4. Extracranial Tumor Sample Collection for Pharmacokinetics**

Optional sampling of readily accessible extracranial metastases will be performed on the day of the removal of the brain metastasis (es), or up to one day before or after the craniotomy if necessary for scheduling. Sampling will consist of an excisional biopsy, core needle biopsy, or a 6 mm punch biopsy. 100 mg to 1 gm of the biopsy material of the extracranial metastasis (es) will be snap-frozen for pharmacokinetic analysis and quantified using an investigative LC-MS/MS method. If the tumor is bloody, the tissue will be blotted on gauze to dry prior to snap freezing in liquid nitrogen. A second portion of the tumor (up to 500 mg) will be inserted into a tissue cassette, embedded in OCT solution, and frozen. A third portion of the tumor (up to 100 mg) will be fixed in formalin for paraffin embedding (FFPE). Additional tumor tissue may be used to establish an immortalized cell line and/or snap-frozen. The remaining portion of any

adjacent “normal” tissue that has been confirmed by the pathologist using frozen sections or the underlying normal tissue that is required to be resected in order to gain access to the underlying metastasis will be processed in a similar fashion. The time of tumor collection will be recorded for comparative pharmacokinetic analyses.

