of the brain and whole-body PET-CT imaging will also be performed between 1 to 3 days prior to surgery. On the day of surgery, blood samples will be collected for pharmacokinetic analysis. Two samples will be collected prior to surgery, and two samples will be collected after surgery; all samples will be separated in time by at least 1 hour. Optional collection of CSF will be obtained in the operating room on the day of brain metastasis resection; this procedure is described in Section 6.5 of the protocol. Portions of the resected brain metastasis(es) that in the clinical judgment of the neurosurgeon performing the operation are not required to be submitted for pathological confirmation of melanoma brain metastasis will be divided into sections to be used for pharmacokinetic, pharmacodynamic, and exploratory translational research studies. Optional collection of an easily accessible extracranial metastasis may be performed after the PET-CT scan and up to 1 day after the removal of brain metastasis(es); which will be similarly divided for studies. The time of collection of brain metastasis, the plasma samples, and the optional extracranial metastasis(es) and CSF will be recorded for the purpose of the pharmacokinetic analysis, as well as the time the last dose of study treatment was taken.

Subjects in either cohort with intracranial and/or extracranial metastases remaining after surgery may resume treatment with the combination of dabrafenib 150 mg BID and trametinib 2 mg once daily no earlier than 72 hours after surgery at the discretion of the Principal Investigator. Subjects continuing on treatment will be evaluated for safety 4 weeks after restarting treatment, and every 4 weeks thereafter. These subjects will be evaluated for efficacy eight weeks after restarting treatment, and every 8 weeks thereafter.

[figure not shown]
Subjects who do not continue treatment after the craniotomy procedure will be evaluated for safety at the discontinuation visit 4 weeks after the craniotomy.

All subjects who permanently discontinue study treatment will be followed for survival and new anti-cancer therapy for a total of two years or until death or the subject wishes to withdraw from further follow-up. The study will be considered closed once the last subject reaches this milestone.

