This trial will prospectively evaluate the levels of dabrafenib and its metabolites that are achieved in melanoma brain metastases, the relationship between the drug levels achieved in the brain metastases and in the plasma, and the activation of the MAPK pathway and other cell signalling networks in the brain metastases. In subjects receiving dabrafenib in combination with trametinib, drug levels of trametinib will also be assessed, where feasible. Subjects may also undergo optional biopsies of readily accessible extracranial tumors (i.e. skin, subcutaneous, superficial lymph nodes) prior to initiating treatment and on the same day as the craniotomy. The activation status of the MAPK and other cellular signalling pathways will be determined in the pre- and post-treatment specimens to determine the degree of pathway inhibition achieved in the extracranial metastases, which will be compared to the activation status of the pathway in the brain metastases at the time of resection. The levels of dabrafenib and its metabolites will also be determined in the available extracranial metastases for comparison to the pharmacodynamic effects, and for comparison to the levels achieved in the brain metastases and the plasma. For subjects who consent to the optional procedure, we will

also determine the levels of dabrafenib and its metabolites in the CSF, which will be collected at the time of the craniotomy, and will be compared to the levels in the plasma and in the brain metastases. Exploratory studies of the activation status of other pro-survival pathways as well as for the prevalence of BRAF and activating mutations in other oncogenes will also be performed on the tissues obtained from the study. The study also incorporates imaging to detect early clinical responsiveness of the brain and extracranial lesions, for correlation with the results of the pharmacokinetic and pharmacodynamic studies, and the pathologic and immunological features of the tumor.

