### 3.1.2. Treatment Duration and Timing Rationale

The goals of the study include both pharmacokinetic and pharmacodynamic evaluations. Thus, the duration of pre-operative treatment is designed to result in surgery prior to significant tumor tissue degradation due to apoptosis and/or necrosis. Based on pharmacokinetic analyses from the FTIH study, dabrafenib exposure decreases with time and is near steady state after about 14 days of dosing. However, two of the dabrafenib metabolites accumulate with repeat dosing due to their long half-life and are generally stable after one week of dosing. Based on these PK data and the analysis of a selected number of tumor tissue biopsies performed between 8 to 15 days of treatment, it is estimated that the ideal duration of treatment will be 7 to 14 days. In the initial phase of the trial, the treatment duration goal will be for 7 days, with 24-48 hour variance allowed for scheduling conflicts. Study treatment will be taken until the evening before surgery. Concentrations of dabrafenib and hydroxyl-dabrafenib should be in the terminal, linear phase during surgery while concentrations of carboxy-dabrafenib and desmethyl-dabrafenib should be fairly constant. This will allow better estimations of brain to plasma equilibrium. A sample quality review will take place after 3 subjects have been treated to allow for evaluation of modifiable treatment logistics and the ability to complete the primary objective of the study. This sample quality review will include an assessment of the quality of the tissue samples from the resected brain and optional extracranial metastases for the planned pharmacokinetic and pharmacodynamic analyses. In addition, the results of the pharmacokinetic analysis of dabrafenib and its metabolites for the first 3 subjects will be reviewed. Adjustments may be made to the duration of the treatment before surgery, and/or the timing of the last dose of dabrafenib that is administered prior to surgery, based on the review of the results by the participating investigators. Subject safety and any unexpected toxicities will also be reviewed. Accrual will continue during this formal review. Additional analyses will be performed after the last patient in the dabrafenib cohort reaches the 4-week post-craniotomy assessment or withdraws from the study, whichever comes first.

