14. Chemistry and hematology evaluations are performed by the central laboratory.
15. PET-CT imaging will be performed on all subjects within 14 days of starting treatment. Imaging is repeated 1-3 days prior to surgery (optimally 1 day prior to surgery). After surgery, disease assessments will be performed by CT will be performed every 8 weeks.
16. Contrast-enhanced MRI will be performed on all subjects within 14 days of starting treatment. Imaging is repeated 1-3 days prior to surgery; day 3 after surgery and every 8 weeks thereafter.
17. A total of 4 PK samples will be obtained on the day of surgery. Two samples should be obtained prior to surgery and separated by at least 1 hr. Two samples should be obtained after surgery and separated by at least one hour. The date and time of PK samples and of the dose taken the evening before must be recorded.
18. Skin photography of new non-melanoma skin lesions or non-melanoma lesions that change during treatment must be obtained at each reassessment while the subject is on study medication.
19. Optional collection of extracranial tumor may be performed after the PET-CT scan and up to 1 day after the removal of brain metastasis(es), and at the time of disease progression
20. 1 genomic DNA Yellow/ACD tube at baseline; 3 x 10cc red top serum tubes and 10 x 10 cc heparin/green top tubes for peripheral blood mononuclear cell PBMC isolation at baseline, Week 4 and 8 post-craniotomy.

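### Three conflicting windows for extracranial tissue let off-day biopsies be set against surgery-day plasma and brain tissue, which may confound dabrafenib and hydroxy-dabrafenib comparisons with time since last dose

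*Protocol*

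**What the plan says.** The protocol states the timing of the on-treatment extracranial sample in three ways.

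- **Same day.** Section 7.4.1 defines the extracranial PK endpoint: drug levels in "samples of extracranial metastases collected on the same day as the brain tumor resection will be determined". The Protocol Summary (Study Design) also says same day, and a later paragraph of section 3 places the biopsies "prior to initiating treatment and on the same day as the craniotomy".
- **One day either side.** Section 7.4.4 allows the day of surgery, "or up to one day before or after the craniotomy if necessary for scheduling". Section 7.5.2 has the same window for pharmacodynamic tissue.
- **From the PET-CT to one day after.** An earlier paragraph of section 3 says that collection "may be performed after the PET-CT scan and up to 1 day after the removal of brain metastasis(es". Table 19 note 19 agrees. Note 15 puts that scan 1 to 3 days before surgery.

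On dosing, section 5.1.3 gives dabrafenib about every 12 hours. Section 3 places the last pre-operative dose on the night before craniotomy and allows no restart for at least 72 hours after surgery. Section 3.1.2 explains the design: "Concentrations of dabrafenib and hydroxyl-dabrafenib should be in the terminal, linear phase during surgery". It expects the carboxy and desmethyl metabolites to be roughly constant.

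On plasma, Table 19 note 17 and section 7.4.5 schedule four samples, all on the day of surgery. Sections 9.1.1 and 9.2.4.1.1 and SAP 2.5.1 plan ratios to plasma. The Protocol Summary and section 3 plan to compare extracranial with brain levels.

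**The concern.** Section 2 treats it as critical to learn whether drug levels in intracranial lesions differ from those in extracranial lesions and plasma. A fair answer needs samples at a similar time since the last dose. For the two analytes expected to be falling at surgery, the wider windows do not ensure this. Tissue taken before surgery is taken during twice-daily dosing. Tissue taken the day after is about 24 hours further off drug. Each would be set against plasma and brain tissue from the day of surgery.

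A difference caused by the clock could then be read as a difference between tissues. The two kinds of off-day sample can also err in opposite directions, so pooling them is not a dependable correction. Under SAP 2.5.3 a tissue value below the quantitation limit becomes zero, so a late sample could be listed as zero because of washout.

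The windows also conflict for the sites: a biopsy that Table 19 permits can breach section 7.4.4, and one that section 7.4.4 permits can fall outside the endpoint in section 7.4.1.

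**Working it through.** The plan states no figure to reproduce. The check sets the provisions side by side and then illustrates the size of the timing effect.

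**Step 1: where each sample sits relative to dosing**

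| Extracranial sample | Permitted by | Dosing state | Scheduled plasma that day |
|---|---|---|---|
| Up to 3 days before surgery | Section 3, Table 19 | On 12-hourly dabrafenib | None |
| Day before surgery | Sections 3, 7.4.4, 7.5.2, Table 19 | On 12-hourly dabrafenib | None |
| Day of surgery | All | Off drug since the previous evening | Four samples |
| Day after surgery | Sections 3, 7.4.4, 7.5.2, Table 19 | About 24 h further off drug, no dose allowed | None |

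**Step 2: does any rule deal with the mismatch?**

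- Section 9.2.4.1.1 lets plasma be interpolated to the time of collection. The scheduled samples all fall on one day, so an off-day biopsy would need extrapolation.
- Section 7.4.5 permits extra PK samples but does not require one with an off-day biopsy.
- Collection and dose times are recorded (sections 3, 7.4.4, 7.4.5), but no rule uses them to restrict or adjust a comparison.
- SAP 2.2 excludes samples only when a collection or dosing date or time is missing. An off-day sample with complete times stays in.

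Followed as written, SAP 2.5.1 could divide off-day tissue by surgery-day plasma.

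**Step 3: size, as an illustration**

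The documents give no half-life. Assume values of 5 to 12 h, single-exponential decline in tissue, and equal true exposure in the tissues compared. The shift for a timing gap Δt is 2^(Δt / t½).

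*Day-after biopsy:* Δt = 24 h with no dose in between. *Pre-surgery biopsy:* under 12-hourly dosing the gap in time since dose is at most about one interval, so Δt runs from 0 (times match) to about 12 h. This takes the resection to fall about 12 h or less after the evening dose; a later operation would widen the gap.

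| Assumed t½ | Day after: 2^(24/t½) | Before surgery, upper limit: 2^(12/t½) |
|---|---|---|
| 5 h | 2^4.8 = 27.9 | 2^2.4 = 5.3 |
| 8 h | 2^3 = 8.0 | 2^1.5 = 2.8 |
| 10 h | 2^2.4 = 5.3 | 2^1.2 = 2.3 |
| 12 h | 2^2 = 4.0 | 2^1 = 2.0 |

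The lower limit for pre-surgery tissue is 2^0 = 1, no shift. A day-after biopsy makes the extracranial level too low relative to plasma and brain. A pre-surgery biopsy soon after a dose makes it too high.

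**Step 4: slow analytes**

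At an assumed half-life of 96 h, 24 h gives 2^0.25 = 1.2-fold, in line with section 3.1.2's expectation for carboxy- and desmethyl-dabrafenib. At 24 h the shift would be 2-fold. Trametinib is not assessed.

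**The case against.** The strongest reply is that the plan has tools for this and that little now depends on it. Section 7.4.5 allows PK samples to be moved or added, section 9.2.4.1.1 allows interpolation, and all the relevant times are recorded. The PK listing shells carry assessment date and time, and the dosing listing carries dose dates and times, so time since last dose can largely be reconstructed. The revision chronology shows that Amendment 3 deliberately allowed one day either side, so the same-day wording may simply not have been updated. The study stopped with six patients, extracranial biopsies are optional, and SAP 2.5.1 plans listings without summaries. The SAP's list of outputs names PK listings for plasma, CSF and brain metastases but none for extracranial tissue.

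Much of this stands as a limit on importance. It does not remove the point: the provisions are permissive, interpolation cannot reach another day, and SAP 2.5.1 still plans individual ratios to plasma for the different sample types if data permit.

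A reader might also infer more than the documents support:

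- *That any off-day sample is wrong by 4- to 28-fold.* Those figures apply only to a day-after biopsy and rest on assumed half-lives.
- *That off-day samples can never have matching plasma.* That is the default schedule; section 7.4.5 permits extra draws.
- *That a direct brain:extracranial ratio is planned.* Section 9.2.4.1.1 and SAP 2.5.1 name ratios to plasma, and section 9.1.1 is ambiguous.
- *That the ratios would measure only sampling delay.* They may be confounded by it, for two of the analytes.

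**Conclusion.** The point holds in a limited form. The protocol contains three incompatible windows, and nothing in the protocol or SAP keeps off-day extracranial tissue from being set against surgery-day plasma or brain tissue. For dabrafenib and hydroxy-dabrafenib, such an extracranial:plasma ratio or brain-versus-extracranial comparison may be confounded by time since last dose. The illustrated shift is about 28- to 4-fold for a day-after biopsy and about 1- to 5-fold for a pre-surgery biopsy, on assumed half-lives of 5 to 12 h and simple exponential decline. Carboxy- and desmethyl-dabrafenib should be little affected, and no conclusion is drawn for trametinib.

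The documents do not show that any off-day biopsy was taken. With at most six patients, optional sampling and no summary analysis, the practical effect is small. It still merits correction because the rule is cheap and, with so few subjects, one mistimed ratio could mislead.

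**What to change.** **Protocol.** Reconcile the collection window across sections 3, 7.4.1, 7.4.4, 7.5.2 and Table 19, including the same-day statement in the Protocol Summary.

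**SAP 2.5.1.** For dabrafenib and hydroxy-dabrafenib, compute the extracranial:plasma ratio, and make any brain-versus-extracranial comparison, only for tissue taken on the day of surgery or with plasma actually drawn at the time of the biopsy. List every off-day sample with hours since last dose: without a ratio for these two analytes, and with a flag on the others.

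**Cost.** This is wording, one listing column derived from times already collected, and a flag. No sample is discarded, but a few optional samples drop out of the ratio for two analytes. Since enrolment has ended, the protocol change cannot alter samples already taken; the SAP rule is the part that affects what is reported.
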